9.6 Data Analyses

Qualitative Data Analysis. We will identify themes through team-level review of transcripts and group discussions.

Quantitative Data Analysis. In the past, researchers have used pilot data to estimate an effect size for future power calculations. Kraemer et al.⁶⁰ emphasized the limitations of this practice due to the likelihood of large standard errors surrounding effect size estimates, and the concern that ultimately, large-scale RCTs should be powered to detect between-group differences considered to be *minimally clinically significant*.

Using data from the pilot RCT, we will examine differences in means and SDs (or frequencies) of key variables (e.g., NAS total score, NAS subscale scores, secondary outcomes, and possible mechanisms) across time points using repeated-measures ANOVA. We will use effect size estimates to characterize differences between groups at each timepoint and will calculate associated 95% confidence intervals of these estimates in order to understand the precision, or lack thereof, of our estimates. We recognize that, due to the likely size of these CIs, these analyses may not permit definitive conclusions.

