To assess within-group changes on outcomes. The primary clinical target (and primary outcome for a subsequent efficacy trial) will be anger dysregulation assessed by the NAS at post-intervention (wk10). Secondary targets (and secondary outcomes for a subsequent efficacy trial) include Aggression (AQ-SF); behavioral infractions, depression (PHQ-9), anxiety (PROMIS Anxiety), and functional impairment (SF-12). We will assess these changes from pre-intervention to post-intervention (wk10), and pre-intervention to follow-up (wk18). ** This is exploratory.**	Endpoint = post-intervention (wk10); follow-up (wk18)	Within-subjects t-tests (e.g., from pre-intervention to post-intervention/wk10, and pre-intervention to wk18). We will conduct analyses separately by treatment group. We will calculate effect sizes (Cohen's d) from pre- to post- treatment/wk10, with corresponding confidence intervals.
Assess within-group changes on anger rumination, decentering, and impulsivity. ** This is exploratory.**	Endpoint = post-intervention (wk10).	Within-subjects t-tests (e.g., from pre-intervention to wk10). We will conduct analyses separately by treatment group.

9.1.2. Description of Assessment Instruments.

All interview and self-report assessment measures were chosen because they have strong psychometric properties for measurement of constructs of interest to the study, and have been used in other NIH-funded clinical trials and prospective studies. With signed releases of information (ROIs) obtained at the baseline assessment, we will supplement interview and self-report data with criminal justice records review to assess for rates of behavioral infractions in prison.

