9.3 Definition of Populations

All data analysis will use the intent to treat population and use all available data. There is no per protocol analysis planned.

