Feasibility and Acceptability—Research Procedures	
Recruitment rate	Average of 6 enrolled per month
Retention rate	80% complete week 10 assessment; 70% complete wk. 18 assessment
Completion of items on assessment instruments	At least 90% of items are completed on each assessment instrument (so each will be valid).

9.5.2 Secondary/ Exploratory Outcomes.

In Phase 2, we will also examine change in key variables over time. This is an exploratory analysis.

Specifically, we will look at change over time the in the following variables. The primary outcome in a subsequent efficacy study is in **bold and underlined**. Secondary outcomes are in standard text. *Potential mechanisms are in italics*.

- **NAS-Provocation Inventory from BL to wk10**; BL to wk18.
- Aggression Questionnaire – Short Form, BL to wk10; BL to wk18.
- Number of behavioral infractions in Prison, BL to wk10; BL to wk18
- PHQ-9, BL to wk10; BL to wk18
- PROMIS Anxiety, BL to wk10; BL to wk18
- SF-12 physical health composite score, BL to wk10; BL to wk18
- SF-12 mental health composite score, BL to wk10; BL to wk18
- *Anger rumination scale, BL to wk10; BL to wk18*
- *Experiences Questionnaire, BL to wk10; BL to wk18*

- *Stroop Color and Word Test, BL to wk10; BL to wk18*

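### Section 9.3 promises intent-to-treat with all available data, but the repeated-measures ANOVA in 9.6 has no missing-data method; if it runs to week 18 on complete cases, it keeps at most 28 of 40 at target retention

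*Combined protocol and SAP*

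**What the plan says.** Section 9.3 sets one rule for every analysis: "All data analysis will use the intent to treat population and use all available data".

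Two methods are named for change over time. Section 9.6 examines key variables "across time points using repeated-measures ANOVA", without listing which time points enter. It adds: "We will use effect size estimates to characterize differences between groups at each timepoint", with 95% confidence intervals. Table 5 (section 9.1.1) specifies "Within-subjects t-tests (e.g., from pre-intervention to post-intervention/wk10, and pre-intervention to wk18", and adds "We will conduct analyses separately by treatment group", with Cohen's d for the change to week 10.

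The retention targets in the target outcomes table of section 9.5.1 are "80% complete week 10 assessment; 70% complete wk. 18 assessment". Week 5 has no target.

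No section names an imputation method, a likelihood method or a missingness assumption. Section 6.2.6 mentions modern statistical methods, but in the context of visits outside the window, and names none. Sections 10.3.5 and 8 (of the Data Safety Monitoring Plan) only check forms and variables for missing values. Sections 8 and 9.5.1 of the protocol continue assessments after a participant stops the intervention. That reduces missing data but does not say how to analyse what remains missing.

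**The concern.** A classical repeated-measures ANOVA needs every visit from every person it includes. Someone seen at baseline, week 5 and week 10 but missed at week 18 is removed entirely, together with a week 10 score that was collected. That is hard to square with a rule to use all available data.

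The week 10 score on the Novaco Anger Scale (NAS) is the named primary outcome of the follow-on trial. Without a rule, two analysts could follow this plan, report different numbers analysed and different NAS changes, and both claim to comply with 9.3. A complete-case estimate also needs stronger assumptions about dropout than a likelihood method does.

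**Working it through.** The plan states no expected number analysed, so there is no figure to reproduce. The check uses the plan's own inputs.

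**Inputs.** 40 randomised (9.2.1); 1:1 allocation, so 20 per arm (Data Safety Monitoring Plan, 7.2); targets of 80% at week 10 and 70% at week 18 (9.5.1). Assumed, because not given: week 5 attendance of 32 to 40, equal retention by arm, and visit correlations of 0.5 to 0.8.

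**Numbers observed.** Week 10: 0.80 × 40 = 32, or 16 per arm. Week 18: 0.70 × 40 = 28, or 14 per arm.

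**Complete cases over all four visits.**
- Maximum: min(n5, 32, 28) = 28.
- Minimum: n5 + 32 + 28 − 80, which is 20, 16 or 12 for n5 = 40, 36 or 32.
- Observed week 10 scores discarded: at least 32 − 28 = 4.
- With baseline and week 10 only: up to 32 kept, none discarded.

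**Paired t-tests.** About 16 pairs per arm at week 10 and 14 at week 18. They leave out 8 and 12 of 40 people, who have no score at that visit. What goes unused is those people's baseline scores and any week 5 scores.

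**Precision between arms.** The 95% half-width for a difference near zero is t × √(2/n). With 16 per arm it is 2.042 × √(2/16) = 0.72 SD. With 14 per arm it is 2.056 × √(2/14) = 0.78 SD.

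**Standard error of within-arm change to week 10, in SDs.** Numbers per arm are 20 at baseline and week 5, 16 at week 10 and 14 at week 18, with nested dropout. Paired: √(2(1 − ρ)/16). Complete-case: √(2(1 − ρ)/14). Here ρ is the baseline–week 10 correlation (r under compound symmetry, r² under AR(1)). The mixed-model figure is generalised least squares with the covariance known.

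| Correlation | Mixed | Paired | Complete-case |
|---|---|---|---|
| Compound symmetry, 0.5 | 0.242 | 0.250 | 0.267 |
| Compound symmetry, 0.8 | 0.154 | 0.158 | 0.169 |
| AR(1), 0.5 | 0.290 | 0.306 | 0.327 |
| AR(1), 0.8 | 0.201 | 0.212 | 0.227 |

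The mixed-model gain at week 10 is 3-5% over paired and 9-11% over complete-case. At week 18 it is 5-8% over paired.

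**Bias in week 10 change if dropout depends on observed scores** (assumed latent correlation d of 0.3 to 0.5).
- Paired bias is d × [φ(z)/0.8] × (r between weeks 5 and 10 − r between baseline and week 5). It is about 0 when the two correlations are equal. With 0.7 and 0.5, it is 0.021 SD at d = 0.3 and 0.035 SD at d = 0.5.
- Complete-case bias, from a two-stage dropout simulation, is about 0.015 to 0.088 SD in absolute size.

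**The case against.** The strongest reply is that the loss to 28 rests on two things the plan does not say: that week 18 is in the same ANOVA, and that incomplete cases are dropped. The contrasts listed in Table 5 and section 9.5.2 are pairwise, baseline to week 10 and baseline to week 18, so a two-visit reading is open. This stands, and 28 must carry its conditions.

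It is also fair that 9.3 states a population. It can be read as an available-case rule covering the between-group effect sizes at each visit. The gap is the missing-data method, not the absence of any population.

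A reader might infer that the paired t-tests breach 9.3 as well. The documents do not support that. The tests use every pair that exists, and 9.3 does not require a modelled value for people not observed. In simulations of 40-person trials, paired and mixed-model bias were nearly equal in two scenarios (−0.003 against −0.004, and −0.015 against −0.016 SD). In a third, with unequal correlations, they were −0.026 and 0.009, with Monte Carlo standard errors of 0.010 to 0.013.

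Finally, section 9.6 itself warns against powering trials on pilot effect sizes and concedes that "these analyses may not permit definitive conclusions". Section 9.1 uses the pilot estimates only alongside larger trials. These points limit the consequences but do not supply the missing method.

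**Conclusion.** The point holds in conditional form and is minor. Fitted to complete cases from baseline to week 18, the ANOVA would not deliver the 9.3 rule. The per-arm figures of 16 and 14 assume equal retention, whereas the targets are overall.

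The precision gains are best-case, because at this sample size the covariance must be estimated. The bias figures depend on dropout strengths that the documents do not give. A reader might go on to infer a biased comparison between arms. That would need dropout to differ by arm, and nothing in the documents shows that it does. Nor are the pilot's main conclusions at risk, since they rest on descriptive statistics and qualitative data. The case for change is that the plan can meet its own rule with the same data.

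**What to change.** In section 9.6, for the continuous outcomes, replace the repeated-measures ANOVA with a REML linear mixed model on all randomised participants with any assessment:

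- Terms: arm, visit, arm × visit, and the gender/facility stratum.
- Covariance: unstructured and pooled across arms, with a prespecified fallback to compound symmetry if the model does not converge.
- Degrees of freedom: Kenward-Roger or Satterthwaite. This matters at n = 40: a check of 600 simulated trials with an unstructured covariance and plain 1.96 limits gave coverage of 92.8-93.8%, with a Monte Carlo standard error of about 1 percentage point.
- Output: within-arm and between-arm estimates at weeks 10 and 18 with 95% confidence intervals, and the number contributing at each visit.
- Standardiser: name the SD that turns these into Cohen's d, for example the pooled baseline SD.

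Keep the Table 5 t-tests by arm as a labelled available-pair supplement. Leave "Number of behavioral infractions in Prison, BL to wk10; BL to wk18" outside this model. It is a count drawn partly from record review, so it may not go missing with visits; summarise it descriptively by arm and period with N stated.

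The cost is wording in 9.6 and Table 5, with no new data. The downsides are a small precision gain, a covariance pooled across arms where Table 5 now analyses the arms separately, and possible simplification of the covariance at n = 40. The unstructured model converged in all 1,200 simulated trials, which had week 5 complete; real data may behave less well.

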Yoga classes. The manualized hatha yoga program will begin with an initial individual session with a yoga teacher to increase motivation for class attendance and self-efficacy for yoga practice between classes. Subsequently, participants will be asked to attend one 60-75 minute class per week for 10 weeks.

Health education. The program consists of information about general health topics. Participants will be asked to attend one 60-75 minute class per week for 10 weeks. Each week will cover a different topic.

Sample Size and Population

Phase 1 of the proposed project will include up to 18 prisoners and 6 representatives from important criminal justice stakeholder groups in focus groups. Also in Phase 1, we will conduct interviews with 3 separate prison administrators as key informants. Because RIDOC administrators may have a supervisory role over other RIDOC stakeholders, we believe it may not be prudent to have them participate in focus groups with other staff. Thus, prison administrators will be interviewed individually and separately as key informants (which are not considered to be human subjects, per the Brown University IRB).

Phase 2 of the proposed project will include 40 prisoners in the pilot. All prisoners will be high in self-reported anger dysregulation. Participants will be prisoners aged 18 to 70. We will recruit 20 men and 20 women to participate.

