5.2 Handling of Study Interventions

5.2.1. Hatha Yoga Intervention.

The yoga intervention will involve an initial individual session with a yoga teacher, designed to increase motivation for yoga class attendance and self-efficacy for adapted yoga practice (see below) between classes. Following the initial individual session, participants will be invited to attend one 60-75 minute yoga class for 10 weeks in the prison facility where they reside. Each class will consist of: breathing exercises, brief guided centering meditation, warm-ups, standing postures, floor postures, an inversion, relaxation, and between-class practice assignments. Classes will emphasize mindfulness, including noticing emotions, thoughts, and physical sensations related to anger, and moderate physical activity. Classes will include some teaching of a relevant yoga theme, such as nonviolence (ahimsa). We will plan themes with input from prisoners and other stakeholders prior to starting classes and rotate through themes. Themes may be introduced via a brief meditation at the beginning of class, and mentioned briefly through class. Between-class practice assignments will be tailored to the prison setting. With input from our stakeholders, we will design a series of brief yoga practices that prisoners can engage in either a) on a daily basis, such as when they wake up or before bed; and b) when they notice that they need to cope with angry or other difficult feelings. Practices may include breathing exercises, brief meditation, and simple poses. We will provide participants with written descriptions and diagrams to assist them with yoga practice. Because each participant will have an individual introduction session with a yoga teacher before beginning the classes, and because sessions are not cumulative, participants can

enter the group at any time (i.e., rolling enrollment). Minimum class size is 1, maximum is 10. We prefer to have a group of at least 4 participants for a group effect, with larger groups (i.e. 8-10) being more cost-effective, of 8-10, but recognize that there will be times that not all participants can attend; thus, we will run the classes as long as 1 participant attends.

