Yoga teachers. The Yoga Alliance is a professional organization which sets standards for yoga teacher training. One can be a Registered Yoga Teacher (RYT) at the 200- or 500-hour level. Experienced Registered Yoga Teachers (E-RYT) at the 500-hour level have at least 4 years of experience and 2000 hours of teaching, and are qualified to train teachers and provide continuing education. All study yoga teachers will be RYTs. We will hire and train 2-4 yoga teachers. Male or female instructors will teach classes in both the RIDOC men's and women's facilities. Teachers will also have study-specific training on research methods, anger and emotion dysregulation, and adverse events with the PIs, and on the yoga manual with our local yoga expert consultant, [name] (E-RYT) and Co-I [name] (RYT). Yoga instructor supervision will include the following: [name], with [name] assistance, will oversee delivery of yoga classes to ensure adherence to the manual and to maintain good quality of instruction. Once trained, teachers will meet twice monthly with [name] and/or [name] for supervision. If an instructor falls below 80% adherence in 3 consecutive classes, we will implement remediation measures, such as observing classes and providing direct instruction to the teacher. Continued non-adherence may be grounds for replacement.

Instructor adherence. We will develop an adherence measure in order to evaluate whether yoga teachers can reliably deliver the manualized program. This adherence measure will have two components: a) a checklist corresponding to the manual to ensure that instructors lead each major component of the class; and b) scales regarding the degree to which the instructor adheres to the style of the class outlined in the manual. (For example, does he/ she repeatedly direct participants to attend to physical sensation in their bodies?). [name] and [name] will train an RA to conduct adherence ratings on audio-recorded yoga classes, as video will not be allowed in the RIDOC. Once [name] and the RA have achieved an acceptable degree of reliability ($r > .80$), the RA will conduct adherence ratings of 20% of classes. [name] and [name] will review ratings with teachers. [name] and/or [name] will rate classes on a monthly basis to test RA reliability against a "gold standard" in an ongoing fashion.

5.2.2. Health Education Control Group.

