To match for attention, the control condition will be a 10-week program that consists of weekly 60-75 minute group classes. In classes, instructors will provide information about general health topics through a variety of means such as slides, handouts, and/or audio and video clips. There will be an emphasis on group discussion of relevant topics; instructors do not just lecture. The core rationale for this course is that good physical health is important for good mental health. In prior research, we have developed and successfully used a manual for teaching this class; the manual will be modified based on feedback from prisoners and prison staff in Phase 1 of this study. Sample class topics are: What to Eat; What Not to Eat; Protecting Your Heart; Physical Activity Guidelines; Diabetes; Cancer Prevention; and Getting a Good Night's Sleep. In

modifying the manual, we will pay attention to making sure that any health-related recommendations are feasible both within prison and for a person on a limited budget in the community. Instructors provide will information and encourage questions but avoid psychotherapeutic techniques or personalized goal-setting. Instructors will give participants readings to explore on their own. Because each week covers a different topic and sessions are not cumulative, participants can enter the group at any time (i.e., rolling enrollment), further providing equipoise with the yoga group. Minimum class size is 1, maximum is 10.

Health education instructors. This class will be taught by health education instructors who have experience working in correctional settings and post-baccalaureate experiences or certification in a relevant health care field. We will hire and train 2 health education instructors. Training procedures will be similar to those used for yoga teachers, with training from Drs. [name] and [name], and additional input from Co-I [name]. To enhance equipoise, similar to the yoga arm, male or female instructors will teach HE classes in the participating RIDOC men's and women's facilities. Although it may be difficult to conceal the fact that this is a control group from instructors, we will encourage instructors to do their best work.

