9.2 Sample Size and Randomization

9.2.1. Sample Size.

This project consists of three phases: In Phase 1, we will conduct focus groups with up to 18 prisoners and 6 prison stakeholders. In Phase 2, we will consent up to 175 prisoners in order to achieve our enrollment goal of 40 prisoners who meet study inclusion for randomization to conditions in the pilot RCT. We will assess feasibility, acceptability, and safety of the interventions and research design, and examine key outcomes within relevant confidence intervals. This phase of the study is not designed to be adequately powered to assess efficacy; rather, it is focused on feasibility, acceptability, and safety.

9.2.2. Treatment Assignment Procedures.

Participants in Phase 2 will undergo randomization. Randomization will be conducted using a blocked stratified randomization scheme. We will stratify patients based on gender and facility (i.e., men’s medium security [n= 20], and women’s combined minimum and medium security [n=20]). Randomization sequences will be generated by computer. Because we cannot bring computers into the prison, we will have someone not associated with the study conceal the group assignments within small opaque envelopes labeled with a number and the strata (for example, male medium 1, male medium 2, etc.). Research assistants will then take the envelopes to the prison, and open them when randomization occurs.

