7.2 Justification of Sample Size

This project consists of two phases: Phase 1 – Focus Groups (N=24), and Phase 2– Feasibility and Pilot Testing (n=40). In phase 1, we will conduct 4 focus groups with a total of 24 participants. This should provide sufficient feedback to modify our current yoga manual specifically for anger dysregulation in prison. In Phase 2, we will conduct a pilot RCT (n = 40), in which participants will be assigned to either weekly hatha yoga or health education classes for 10 weeks (on a 1:1 basis). We will assess feasibility, acceptability, and safety of the interventions and research design, and examine key outcomes (anger dysregulation, aggression) within relevant confidence intervals. This phase of the study is not designed to be

adequately powered to assess efficacy; rather, it is focused on feasibility, acceptability, and safety.

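### The nominal 95% CIs for the exploratory outcomes ignore shared classes and instructors and omit the facility stratum, so they are somewhat too narrow if outcomes correlate within class

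*Combined protocol and SAP*

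**What the plan says.** **Design.** The Précis (Sample Size and Population) says "We will recruit 20 men and 20 women to participate". Section 7.2 of the data and safety monitoring plan has participants "assigned to either weekly hatha yoga or health education classes for 10 weeks (on a 1:1 basis". Randomisation is of individuals, in blocks, and Section 9.2.2 says "We will stratify patients based on gender and facility": one men's and one women's facility, 20 people each.

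**Delivery.** Classes are held in the participant's own facility (Section 3), with at most 10 per class and rolling entry in both arms (Sections 4.4.5 and 5.2). On staffing, Section 5.2.1 says "We will hire and train 2-4 yoga teachers" and Section 5.2.2 says "We will hire and train 2 health education instructors". On yoga class size, Section 5.2.1 adds "We prefer to have a group of at least 4 participants for a group effect".

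**Analysis.** Section 9.6 plans repeated-measures ANOVA and continues: "We will use effect size estimates to characterize differences between groups at each timepoint and will calculate associated 95% confidence intervals of these estimates". Table 5 (Section 9.1.1) plans paired t-tests separately by arm, with Cohen's d from pre-intervention to "treatment/wk10, with corresponding confidence intervals". Neither section mentions class, instructor, facility, an ICC or an adjusted standard error. Section 9.6 concedes that the CIs may be too wide for definitive conclusions.

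**The concern.** Individuals are randomised but then treated in groups. People who share a class and an instructor may change together, through the instructor's skill, the mix of attendees or events in that room. Paired t-tests, a standard repeated-measures ANOVA and the usual CI for Cohen's d assume that participants vary independently, so any shared component is left out of the error term.

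Section 9.6 gives the CIs one task: to show how precise, or imprecise, the estimates are. Section 9.1 adds that pilot data will help to indicate a plausible range of effect sizes for a later trial, alongside results from larger trials. Intervals that leave out a source of variance do that task less well. The caveat in Section 9.6 warns that the intervals will be wide. It does not warn that they may be narrower than they should be.

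The facility stratum is a separate omission and acts in the opposite direction for the between-arm comparison.

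**Working it through.** The plan states no CI width, SD, ICC or power, so there is no figure of its own to reproduce. The check asks how far a nominal 95% CI would be off.

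**Inputs from the documents**
- 40 randomised 1:1, so n = 20 per arm (Précis; monitoring plan 7.2).
- 2 facilities x 2 arms = 4 class streams, 40/4 = 10 people each. This is derived, not stated.
- Enrolment over about 7 months (Section 3), classes for 10 weeks, rolling entry.
- Retention targets of 80% at week 10 and 70% at week 18 (target-outcomes table in 9.5.1), so about 16 and 14 per arm, or 8 and 7 per stream.

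**Assumed:** ICC 0.02, 0.05 or 0.10.

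**Cluster size m**
- Upper case: the whole stream shares an effect, for example through one instructor; m = 10.
- Rolling-entry case: only concurrent classmates share an effect. Accrual per stream is 40/7/4 = 1.43 a month. Ten weeks is 10/(52/12) = 2.31 months, so about 1.43 x 2.31 = 3.3 people are present together. I use m = 4, slightly on the high side.

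**Formulas**
- Design effect DE = 1 + (m-1) x ICC.
- Between-arm half-width for d near 0 = 1.96 x sqrt(2/20 x DE). With DE = 1 this is 0.62.
- Coverage of the unadjusted interval = 2 x Phi(1.96/sqrt(DE)) - 1.

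| ICC | DE, m=4 | Half-width | Coverage | DE, m=10 | Half-width | Coverage |
|---|---|---|---|---|---|---|
| 0.02 | 1.06 | 0.64 | 94% | 1.18 | 0.67 | 93% |
| 0.05 | 1.15 | 0.66 | 93% | 1.45 | 0.75 | 90% |
| 0.10 | 1.30 | 0.71 | 91% | 1.90 | 0.85 | 84% |

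Simulated t-interval coverage with four streams of 10 agrees for the upper case: about 90% at ICC 0.05 and 84% at 0.10.

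**Within arm.** For a standardised pre-post change with n = 20, the half-width is t(19)/sqrt(20) = 0.47. Multiplying by sqrt(DE) gives 0.48, 0.50 and 0.53 for m = 4, and 0.51, 0.56 and 0.65 for m = 10.

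**With the retention targets.** At week 10 (16 per arm, m = 8) the between-arm half-width goes from 0.69 to 0.74, 0.81 and 0.90. At week 18 (14 per arm, m = 7) it goes from 0.74 to 0.78, 0.84 and 0.94.

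**Facility.** Allocation is balanced within facility, so a facility difference in the outcome largely cancels from the arm contrast. If it is not modelled, it stays in the residual variance and widens the between-arm CI. In a simulation with concurrent clusters of 3-4, an assumed facility difference of 0.5 SD and no facility term, unadjusted coverage is about 95%, 94% and 93% at ICC 0.02, 0.05 and 0.10. With no facility difference it is about 94.5%, 93.5% and 92%.

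**Can the pilot estimate the ICC?** Four stream means, less one intercept and one arm effect, leave 2 df; a facility effect leaves 1. In a simulation with arm as the only fixed effect and a true ICC of 0.05, 95% of estimates fall between -0.11 and 0.34, and about 47% are zero or negative.

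**The case against.** The best defence is that these outcomes are labelled exploratory, no power is claimed, and the later go/no-go decision rests on the feasibility targets. Section 9.6 itself argues against sizing a trial from pilot effects. All of that stands and limits the consequence. It does not make the intervals right for the purpose that Section 9.6 gives them.

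Four stronger readings are tempting, and the documents do not support them:

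- *The intervals are known to be too narrow.* No width is stated, independence is implied by the choice of methods and by silence, and the ICC is assumed. At ICC 0.01 the understatement of width is only 1% to 4%.
- *Coverage is 84%.* That needs both the highest assumed ICC and a whole stream acting as one cluster. Rolling entry makes the smaller figures more likely for classmate effects, although it does not dilute an instructor shared across a stream.
- *The protocol already expects correlated outcomes.* The class-size preference in Section 5.2.1 concerns delivery, and classes run even with one attendee. Section 7.1 says discussion is kept low in yoga. The wording makes a shared effect plausible and goes no further.
- *The pilot should deliver an ICC for the next trial.* Four streams, confounded with facility, gender and probably instructor, cannot give a usable one.

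**Conclusion.** The point holds as a conditional one. The planned CIs in Section 9.6 and Table 5 leave out class and instructor variation, and the between-arm model leaves out the randomisation stratum. If within-class correlation is positive, nominal 95% intervals cover about 91-94% under rolling entry, and 84-93% in the upper case, over assumed ICCs of 0.02 to 0.10. Omitting facility works the other way for the between-arm CI and may offset part of this, so it should not be read as another reason why those intervals are too narrow.

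The result rests on the assumed ICCs, on the inferred structure of four streams of about 10, and on the plan's own accrual period. The change is worth making because it is cheap and serves the stated use of the intervals. It does not bear on the primary feasibility, acceptability and safety outcomes.

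**What to change.** In Section 9.6 and Table 5:

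1. Include facility, the randomisation stratum, as a fixed effect in the between-arm model, and note that leaving it out widens the between-arm CI.
2. Record class stream and instructor for each participant, coded so that the statistician stays blind. Report each between-arm and pre-post CI twice: unadjusted, and with its half-width multiplied by sqrt(1 + (m-1) x ICC) at ICC 0.02, 0.05 and 0.10. Do this for m of about 4 and for the stream size actually analysed.
3. State that the unadjusted CIs are conditional on these classes and instructors.

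Do not use an ICC observed in this pilot to size the next trial.

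**Cost.** A few sentences and a few lines of code. Attendance dates are already captured (Section 10.1), and class recordings are labelled by class type, instructor and date (Section 7.1). Design, sample size and participant burden do not change. The downside is that the reported intervals become wider and rest on an assumed ICC.
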